Neuropathy	
 • Grade 2 treatment emergent neuropathy with pain or Grade 3 neuropathy. Continue to dose. If neuropathy persists for more than two weeks hold carfilzomib until resolved to ≤ Gr 2 without pain. Then restart at next dose level reduction. • Grade 4 neuropathy. Discontinue protocol therapy
Congestive Heart Failure	Any subject with symptoms of congestive heart failure, whether or not drug related, must have the dose held until resolution or return to baseline. After which, treatment may continue at reduced dose or patient may be withdrawn from therapy.

3.3.4 Dose Reductions: Extended Dosing Phases I and II

	Lenalidomide
Baseline dose	10 mg daily on Days 1-21 of 28 day cycle
One level dose reduction	5 mg daily on Days 1-21 of 28 day cycle

3.3.5 Hematologic Toxicity: Extended Dosing Phases I and II

3.3.5.1 On day 1 (or within 7 days prior to day 1) of every third cycle during extension phase, patients must meet the following criteria or dose modify based on dose reductions in

table 3.3.4:

- ANC $\geq 1.0 \times 10^9/L$
- Platelet count $>50 \times 10^9/L$ during cycles 9 and beyond

If these conditions are not met on Day 1 of every third cycle, treatment will not be initiated until the toxicity has resolved. If there is no resolution after 2 weeks of withholding treatment or up to 3 weeks for infection related treatment, the subject will go off therapy.

3.3.5.2 If a patient develops thrombocytopenia or neutropenia during the cycle, then the following actions would take place (see Thrombocytopenia/Neutropenia table below).

Thrombocytopenia	Lenalidomide
Fall to $< 25 \times 10^9/L$	Hold Lenalidomide, follow CBC weekly. Hold prophylactic anti-coagulation.
Return to $\geq 25 \times 10^9/L$	Resume lenalidomide at next dose reduction if deemed drug related
Subsequent fall to $< 25 \times 10^9/L$	Hold Lenalidomide. Hold prophylactic anti-coagulation
Return to $\geq 25 \times 10^9/L$	Patient will go off therapy if deemed drug related

Neutropenia (Absolute Neutrophil Count)	Lenalidomide
Falls to $< 0.5 \times 10^9/L$ or to $< 1.0 \times 10^9/L$ with fever	Hold Lenalidomide. Add filgrastim if Grade 3 with fever (single temperature of 38.3o or sustained temperature of 38o for > 1 hour) or Grade 4. Follow CBC weekly
Returns to $\geq 1.0 \times 10^9/L$	Resume Lenalidomide at next dose reduction.
Subsequent drop to $< 0.5 \times 10^9/L$ or to $< 1.0 \times 10^9/L$ with fever	Hold Lenalidomide. Add filgrastim if Grade 3 with fever or Grade 4. Follow CBC weekly
Returns to $\geq 1.0 \times 10^9/L$	Patient will go off therapy if deemed drug related

3.3.6 Non-Hematologic Toxicity- Extended Dosing Phase

3.3.6.1 Toxicity \geq grade 3 will require study drug to be held until resolved to \leq Grade 1 or baseline unless specified below.

3.3.6.2 Once toxicity has resolved \leq grade 1 or baseline, subsequent doses will be reduced at next dose level (according to table in Section 3.3.4) if the adverse event was deemed to be treatment related by the PI. If the adverse event was deemed to be unrelated to treatment, the patient may continue the full dose. In the case of renally adjusted doses, dosing modifications are made according to table below.

3.3.6.3 Readily reversible electrolyte and metabolic abnormalities or infections controlled by appropriate therapy are exempt.

Common Lenalidomide Toxicities	Dosing Modifications
Non Blistering Rash	
 • If Grade 3, hold lenalidomide dose and restart at next dose reduction once rash improves to ≤ Grade 1 • If Grade 4, discontinue lenalidomide and remove patient from therapy
Blistering Rash (Any Grade)	Discontinue lenalidomide and remove patient from therapy
Venous thrombosis/embolism	Hold lenalidomide and start therapeutic anticoagulation. Restart lenalidomide at investigator's discretion at current dose level.
Renal Dysfunction CrCl based on Cockcroft-Gault formula: $CrCl = (140 - Age) \times Mass \text{ (in kilograms)} \times [0.85 \text{ if Female}] \times Serum \text{ Creatinine (in mg/dL)}$	
 • CrCl 31-60 ml/min – Dose reduce lenalidomide to 10 mg daily from Days 1-21 • CrCl ≤ 30 mL/min (not requiring dialysis) – Dose reduce Lenalidomide to 15 mg every 48 hours and see carfilzomib dosing below. • CrCl ≤ 30 mL/min (requiring dialysis) – Decrease Lenalidomide to 5 mg daily and on dialysis days dose lenalidomide after dialysis.

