3.3 DOSE MODIFICATIONS

3.3.1 Dose Reductions: Induction Phase

	Lenalidomide	Carfilzomib	Dexamethasone Cycles 1-4	Dexamethasone Cycles 5-8
Baseline dose	25 mg daily on Days 1-21 of 28 day cycle	36 mg/m ²	20 mg	10 mg
One level dose reduction	20 mg daily on Days 1-21 of 28 day cycle	27 mg/m ²	10 mg	4 mg
Two level dose reduction	15 mg daily on Days 1-21 of 28 day cycle	20 mg/m ²	4 mg	0 mg
Three level dose reduction	10 mg daily on Days 1-21 of 28 day cycle		0 mg	
Four level dose reduction	5 mg daily on Days 1-21 of 28 day cycle			

3.3.1.1 If more than 2 dose reductions are required with Carfilzomib, study treatment will be discontinued and the patient will go off therapy.

3.3.1.2 If there is no resolution of toxicity after 2 weeks of withholding treatment or up to 3 weeks for infection related treatment, the subject will go off therapy

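### The extended-phase renal rows in 3.3.6 repeat the induction lenalidomide doses: from 10 mg the CrCl 31-60 row changes nothing, and for a patient already at 5 mg no row lowers the dose

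*Combined protocol and SAP*

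**What the plan says.** Section 3.3.1 gives the induction lenalidomide baseline as "25 mg daily on Days 1-21 of 28 day cycle". Section 3.3.4 gives the extended-phase baseline as "10 mg daily on Days 1-21 of 28 day cycle" and a single reduction level, "5 mg daily on Days 1-21 of 28 day cycle".

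For renal dysfunction in the extended phase, 3.3.6.2 points away from that ladder: "In the case of renally adjusted doses, dosing modifications are made according to table below". The table in 3.3.6 then has three rows:

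- CrCl 31-60 mL/min: "Dose reduce lenalidomide to 10 mg daily from Days 1-21".
- CrCl 30 mL/min or below, no dialysis: "Dose reduce Lenalidomide to 15 mg every 48 hours and see carfilzomib dosing below".
- CrCl 30 mL/min or below, on dialysis: "Decrease Lenalidomide to 5 mg daily and on dialysis days dose lenalidomide after dialysis".

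The same three doses appear in the induction table in 3.3.3.

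A patient can reach the 5 mg level before any renal problem arises. After thrombocytopenia in the extended phase, for example, 3.3.5 says "Resume lenalidomide at next dose reduction if deemed drug related".

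**The concern.** The renal doses stay fixed while the baseline beneath them falls from 25 mg to 10 mg. An instruction worded as a reduction may then reduce nothing, or may name more drug than the patient is taking. The second row also refers the reader to carfilzomib dosing, although 3.2.2.1 gives carfilzomib only in Cycles 1-8 and nothing in 3.3.6 covers it. That suggests the rows were carried over from induction without being re-fitted to the lower dose.

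At stake is dosing safety for patients whose renal function falls during Cycles 9-32, which is 32 - 9 + 1 = 24 cycles if 3.3.6 is read as covering both extended phases. Routine chemistry is scheduled only every third cycle (3.3.7.2), or 3 x 28 = 84 days, so a dose taken from this table could stand for three cycles unless extra tests are ordered under 3.3.7.6.

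**Working it through.** The plan states no figure for this point, so there is none to reproduce. The check compares lenalidomide per 28-day cycle under each row with the three possible starting doses.

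**Starting doses** (daily dose x 21 days)

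- Induction baseline (3.3.1): 25 x 21 = 525 mg
- Extended baseline (3.3.4): 10 x 21 = 210 mg
- Extended reduced level (3.3.4): 5 x 21 = 105 mg

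**Renal rows** (dose x number of doses). The first row states Days 1-21. The other two state no window, so both a 21-day and a 28-day reading are shown. Every-48-hour dosing within Days 1-21 gives 11 doses if it starts on Day 1 (Days 1, 3, ..., 21) and 10 if it starts on Day 2 (Days 2, 4, ..., 20). Over 28 days it gives 14.

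| Row and reading | mg per cycle | Change from 525 mg | Change from 210 mg | Ratio to 105 mg |
|---|---|---|---|---|
| CrCl 31-60 | 10 x 21 = 210 | -60% | 0% | 2.00 |
| CrCl <=30, no dialysis, Days 1-21, 10 doses | 15 x 10 = 150 | -71.4% | -28.6% | 1.43 |
| CrCl <=30, no dialysis, Days 1-21, 11 doses | 15 x 11 = 165 | -68.6% | -21.4% | 1.57 |
| CrCl <=30, no dialysis, continuous, 14 doses | 15 x 14 = 210 | -60% | 0% | 2.00 |
| CrCl <=30, dialysis, Days 1-21 | 5 x 21 = 105 | -80% | -50% | 1.00 |
| CrCl <=30, dialysis, all 28 days | 5 x 28 = 140 | -73.3% | -33.3% | 1.33 |

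Change = mg per cycle / starting mg - 1. Ratio = mg per cycle / 105.

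**Reading the table**

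- From 25 mg, every row is a large cut (60% to 80%). The rows work as reductions in induction.
- From 10 mg, the CrCl 31-60 row changes nothing. The non-dialysis row cuts 21% to 29% if Days 1-21 applies and nothing if dosing is continuous; on the continuous reading, CrCl 30 or below gets the same cycle total as CrCl 31-60. The dialysis row cuts 33% to 50%.
- From 5 mg, no row is below the current dose on any reading. Two rows are above it.

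**The case against.** The strongest reply is that the rows are absolute doses for each CrCl band, not steps down from a baseline. Induction already accepts 10 mg on Days 1-21 at CrCl 31-60, given with carfilzomib and dexamethasone. A patient on 10 mg of lenalidomide alone is already at that dose, and no further cut need be expected. This stands. The documents do not show that 10 mg is too much in this band, so a reader who infers an unsafe dose there goes beyond the text. Only the reduction wording fits badly.

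A reader might also infer that the 15 mg row escalates treatment from the 10 mg baseline. It does not: 15 mg every 48 hours averages 7.5 mg per day, and the cycle total never exceeds 210 mg. The continuous reading also sits awkwardly with a phase scheduled at 21 of 28 days (3.2.5, 3.3.4). Nor is it right that the table never reduces the dose, because the dialysis row is a real cut from 10 mg.

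For the patient at 5 mg, the reply is that two events are needed (a reduction to 5 mg, then a fall in CrCl) and that no sensible prescriber would raise a dose under an instruction to lower it. Prescribing is monthly by NIH physicians (3.2.5, 3.2.6), extra tests are allowed (3.3.7.6), and 3.5.1 allows removal for unresolved toxicity or at the investigator's discretion. These points lower the risk but do not supply the missing rule. The hold for grade 3 or higher toxicity in 3.3.6.1 is a less certain safeguard, since it gives way where the table specifies something else, and the table does specify renal dysfunction.

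The absolute-dose reading does not settle the missing day windows, the carfilzomib reference or the patient at 5 mg.

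**Conclusion.** The point holds in a limited form. The three renal doses match those of induction, 3.3.6.2 makes them govern renal dosing, and the carfilzomib reference supports carry-over, though carry-over remains an inference. The clear fault is at the 5 mg level: read literally, the first two rows give 1.43 to 2.0 times the current cycle dose and the dialysis row gives 1.0 to 1.33 times, so a rule meant to lower the dose yields an increase or no cut. From 10 mg, one row is neutral and possibly intended, one depends on an unstated window, and one is a true reduction.

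The ranges rest on two assumptions: an unstated window means either Days 1-21 or all 28 days, and every-48-hour dosing starts on Day 1 or Day 2. The 84-day interval further assumes that the routine chemistry panel includes creatinine.

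Importance is minor. Entry requires CrCl of at least 60 mL/min (2.1.1.2), so only patients whose clearance falls later are affected, and the documents do not say how many remain on extended dosing. The primary endpoint covers neurologic toxicity in the first two cycles, so neither it nor the sample size is touched.

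**What to change.** In 3.3.6:

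- (a) Add a sentence such as: *A renal adjustment must not raise the patient's total lenalidomide dose per cycle above the current level; a patient already at 5 mg stays at or below 5 mg on Days 1-21, or is held.*
- (b) State Days 1-21 in both rows for CrCl 30 or below. From 10 mg, the non-dialysis row then gives 150-165 mg and the dialysis row 105 mg.
- (c) Delete the reference to carfilzomib dosing.
- (d) Have the clinical team confirm whether 10 mg, and 15 mg every 48 hours, are intended as absolute renal doses in this phase. If they are, say so and drop the reduction wording from the CrCl 31-60 row.

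The cap in (a) should apply to the cycle total, not to each dose. No extended-phase dose exceeds 10 mg, so a per-dose cap would make the 15 mg row unusable and prejudge the answer to (d). The documents do not support a specific replacement dose, and none is proposed.

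The cost is a short edit to one table, one added sentence and one clinical question. Nothing changes in the sample size, the primary endpoint or the analysis.

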3.3.7 Monitoring

- 3.3.7.1 Patients will be observed in the hospital for administration of cycle 1 Days 1 and 2 of therapy.
- 3.3.7.2 Routine labs (cbc, chemistry panel 14, LDH, magnesium, uric acid, phosphate) will be performed on Day 1, 2, 8, 15, and 22 of cycle 1 and Day 1 (or within 2 days prior to day 1) of each cycle during cycles 1-8 and on Day 1 (or within 7 days prior to day 1) of every third cycle during extension phases I and II.
- 3.3.7.3 Myeloma tests include serum protein electrophoresis, serum immunofixation, serum free light chains, quantitative immunoglobulins, beta-2 microglobulin and will be performed at baseline and Day 1 (or within 2 days prior to day 1) of each cycle in the induction phase and on Day 1 (or within 7 days prior to day 1) of every third cycle during extension phase I and II. Subsequent serum immunofixation will only be performed on those patients clinically indicated.
- 3.3.7.4 Random urine sample for protein electrophoresis (UPEP) and immunofixation to assess for monoclonal protein in the urine (Bence-Jones proteinuria) to be performed at baseline, day 1 (or within 2 days prior to day 1) of each cycle during cycles 1-8, and day 1 (or within 7 days prior to day 1) of every third cycle during extension phase I and II. If patient obtains CR, then a 24 hour UPEP will be performed to confirm CR status. In patients whose measurable disease is best determined by measuring Bence-Jones protein quantification, a 24-hr UPEP will be performed at baseline, day 1 of each cycle 1-8, and day 1 of every third cycle during extension phase I and II. Otherwise, 24-hr UPEP Bence-Jones quantification will be estimated from random UPEP specimens performed at baseline, day 1 of each cycle 1-8, and day 1 of every third cycle during extension phase.
- 3.3.7.5 Patients will have clinic visits with H&P or standard progress notes assessing for toxicity/side effects on Day 1, 2, 8, 15, and 22 of cycle 1 and Day 1 of each cycle during cycles 1-8 and on Day 1 of every third cycle during extension phases I and II.

(This can be delayed up to one week per PI discretion for clinical and/or logistical reasons).

- 3.3.7.6 Additional laboratory studies and clinic visits will be performed if clinically indicated.
- 3.3.7.7 FDG-PET scan will be performed on patients in the Molecular Imaging Department at baseline, during cycles 1-8 if patient obtains CR or at the end of cycle 8 if no CR is achieved, during cycles 9-20 if patient obtains CR or at the end of cycle 20 if no CR is achieved, and during cycle 21 and beyond if patient obtains CR or at treatment termination. During extension phase lenalidomide, FDG-PET are optional for those patients that are MRD negative at the end of cycle 8 regardless of response. At PI discretion, patient may be asked to have an additional PET-CT scan and/or DW-MRI at progression. The radiation dose from the procedure will be a maximum of 2.1 rem per year; this is within the RSC guidelines of 5.0 rem per year for adults.
- 3.3.7.8 With amendment P, patients who remain on study will be asked to undergo DW-MRI on an annual basis, however, these will not be mandatory.
- 3.3.7.9 During lenalidomide extension phases I and II, FCBP patients will still be required to have pregnancy testing as outlined in [Appendix A](#). Local treating physicians will be required to submit results to NIH clinical center for review.

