3.2 DRUG ADMINISTRATION

3.2.1 Induction Phase: Cycles 1-8 with 28 day cycles

3.2.2 Agents

3.2.2.1 Carfilzomib

- Cycle 1: 20 mg/m² IV infusion over 30 minutes on days 1 and 2, then 36 mg/m² IV on days 8, 9, 15, and 16
- Cycle 2-8: 36mg/ m² IV infusion over 30 minutes on days 1, 2, 8, 9, 15, and 16

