3.3.2 Hematologic Toxicity: Induction Phase

3.3.2.1 Due to the nature of the disease originating in the bone marrow, events occurring within the first two cycles of treatment and deemed to be due to disease burden will be exempt from dose reductions at the discretion of the investigator.

3.3.2.2 On day 1 of each new cycle (or day 1 of every third cycle during extension phase), patients must meet the following criteria or dose modify based on dose reductions in table 3.3.1:

- ANC $\geq 1.0 \times 10^9/L$
- Platelet count $\geq 75 \times 10^9/L$ during cycles 1-8; Platelet count $>50 \times 10^9/L$ during cycles 9 and beyond

3.3.2.3 If these conditions are not met on Day 1 of a new cycle, a new cycle of treatment will not be initiated until the toxicity has resolved. If there is no resolution after 2 weeks of withholding treatment or up to 3 weeks for infection related treatment, the subject will go off therapy.

3.3.2.4 If the investigator chooses to dose reduce according to table 3.3.1, the investigator will determine which drug will be modified based on side effect profile and clinical judgment.

3.3.2.5 If a patient develops thrombocytopenia or neutropenia during the cycle, then the following actions would take place (see Thrombocytopenia/Neutropenia table below).

Thrombocytopenia	Lenalidomide	Carfilzomib
Fall to $< 25 \times 10^9/L$	Hold both Lenalidomide and Carfilzomib, follow CBC weekly. Hold prophylactic anti-coagulation.	

Thrombocytopenia	Lenalidomide	Carfilzomib
Return to $\geq 25 \times 10^9/L$	Resume lenalidomide at next dose reduction	Resume carfilzomib at full dose.*
Subsequent fall to $< 25 \times 10^9/L$	Hold both Lenalidomide and Carfilzomib, follow CBC weekly. Hold prophylactic anti-coagulation.	
Return to $\geq 25 \times 10^9/L$	Resume lenalidomide at next dose level reduction	Resume carfilzomib at full dose.*

*Carfilzomib may be dose reduced at the clinical discretion of investigator

Neutropenia (Absolute Neutrophil Count)	Lenalidomide	Carfilzomib
Falls to $< 0.5 \times 10^9/L$ or to $< 1.0 \times 10^9/L$ with fever	Hold Lenalidomide and Carfilzomib. Add filgrastim if Grade 3 with fever (single temperature of 38.3° or sustained temperature of 38° for > 1 hour) or Grade 4. Follow CBC weekly	
Returns to $\geq 1.0 \times 10^9/L$	Resume Lenalidomide at next dose reduction.	Resume Carfilzomib at full dose.*

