- p. Variations of +/- 3-14 days of scheduled visits are permitted. For patients who choose to undergo stem cell harvest, next cycle may be delayed for up to 5 weeks. In the follow up phase, patients may be allowed to "skip" appointment visits at the discretion of the PI.
- q. Repeat myeloma tests at treatment termination.
- r. Within 7 days prior to D1 of each cycle
- s. May be delayed up to 7 days per PI discretion for clinical or logistical reasons
- t. Every attempt should be made to have all subjects complete a safety visit approximately 30 days following the last dose of study therapy. If subjects cannot return to clinic, this may be done by phone.
- u. With amendment P, patients will be offered DW-MRI on an annual basis; these are optional. Diffusion weighted MRI (DW-MRI) will also be performed at the discretion of the PI. DW-MRI will be performed by standard techniques in the NCI Molecular Imaging Branch.

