4 CONCOMITANT MEDICATIONS/MEASURES

4.1 TUMOR LYSIS SYNDROME

4.1.1 Hydration and Fluid Monitoring:

- Oral hydration: All subjects must be well hydrated (i.e., volume replete). Begin oral hydration equal to approximately 30 mL/kg/day (~6–8 cups of liquid per day), starting 48 hours prior to the planned first dose of carfilzomib. Compliance must be reviewed with the subject and documented by the site personnel prior to initiating treatment with carfilzomib; treatment is to be delayed or withheld if oral hydration is not deemed to be satisfactory.

- IV hydration: 500 mL (250 mL before & 250 mL after carfilzomib) OR 1000 mL (500 mL before & 500 mL after carfilzomib) of normal saline or other appropriate IV fluid formulation must be given before *and* after each carfilzomib dose during Cycle 1 D1 and D2. Total volume will be determined at the discretion of clinician and volume status of patient. If lactate dehydrogenase (LDH) or uric acid is elevated at Cycle 2, Day 1, then the recommended IV hydration should be repeated for Cycle 2. The goal of the hydration program is to maintain robust urine output, (e.g., ≥ 2 L/day). Subjects should be monitored periodically during this period for evidence of fluid overload.
- In subjects considered to be still at risk for TLS at completion of Cycle 1, hydration should be continued into subsequent cycles if clinically indicated.

4.1.2 Laboratory Monitoring:

- Appropriate chemistries, including creatinine, and complete blood counts (CBC) with platelet count should be obtained and reviewed prior to carfilzomib dosing. Results of laboratory studies must be reviewed and deemed acceptable prior to administering the carfilzomib dose.
- Subjects with laboratory abnormalities consistent with lysis of tumor cells (e.g., serum creatinine $\geq 50\%$ increase, LDH ≥ 2 -fold increase, uric acid $\geq 50\%$ increase, phosphate $\geq 50\%$ increase, potassium $\geq 30\%$ increase, calcium $\geq 20\%$ decrease) prior to dosing should not receive the scheduled dose

4.1.3 Clinical Monitoring:

- Signs and symptoms indicative of TLS, such as fevers, chills/rigors, dyspnea, nausea, vomiting, muscle tetany, weakness, or cramping, seizures, and decreased urine output.
- Patients will be admitted to the inpatient hospital and observed while receiving Cycle 1 Days 1 and 2 of therapy.

4.1.4 Management:

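### Section 4.1.2 asks for reviewed labs before carfilzomib dosing, but in cycles 2-8 labs are scheduled on Day 1 only, leaving 28 of 48 planned doses with no scheduled lab

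*Combined protocol and SAP*

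**What the plan says.** Section 3.2.2.1 gives carfilzomib in cycle 1 on "days 1 and 2, then 36 mg/m² IV on days 8, 9, 15, and 16", and in cycles 2-8 as "IV infusion over 30 minutes on days 1, 2, 8, 9, 15, and 16".

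Section 3.3.7.2 places routine labs, including the blood count and chemistry panel, on "Day 1, 2, 8, 15, and 22 of cycle 1 and Day 1 (or within 2 days prior to day 1) of each cycle" for the induction phase. The Routine Labs row of the calendar (Section 3.4) marks the same days. The précis describes routine blood work in induction as monthly, which fits cycles 2-8. Section 3.3.7.6 leaves room for further tests on clinical grounds.

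Section 4.1.2, under tumor lysis syndrome, says that chemistries and "complete blood counts (CBC) with platelet count should be obtained and reviewed prior to carfilzomib dosing". It continues: "Results of laboratory studies must be reviewed and deemed acceptable prior to administering the carfilzomib dose". Neither sentence names a cycle. The IV hydration rule just before it, in Section 4.1.1, is expressly tied to the first two days of cycle 1.

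Section 3.3.2.5 sets the mid-cycle holds: "If a patient develops thrombocytopenia or neutropenia during the cycle, then the following actions would take place". The triggers are platelets below 25 × 10⁹/L, or neutrophils below 0.5 × 10⁹/L (below 1.0 with fever). For platelets the action begins "Hold both Lenalidomide and Carfilzomib, follow CBC weekly", so weekly counts start only once a fall has been found.

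**The concern.** A site that works from the calendar will take no blood on days 8, 9, 15 or 16 of cycles 2-8, yet Section 4.1.2 reads as if results should be in hand before carfilzomib is given on those days. Two things are at stake.

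The first is the safety check. The Section 3.3.2.5 holds, which for platelets also stop prophylactic anticoagulation, need a mid-cycle count to trigger them. In cycles 2-8 none is scheduled.

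The second is reporting. The primary objective is toxicity in general, with neuropathy as one part, so hematologic toxicity will be described. If counts between Day 1 visits are taken at some visits and not others, the cytopenia rates will depend partly on who was tested.

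**Working it through.** **The plan's own design figure.** The documents give no figure for lab coverage. The only design calculation is in Section 10.2: at least 5 of 45 patients with grade 3 or worse neurologic toxicity. With X ~ Binomial(45, p), P(X ≥ 5) is 7.29% at p = 0.05 and 82.52% at p = 0.15. This reproduces the stated 7.3% and 82.5%. X counts neurologic events in the first two completed cycles, and no blood count enters it. The early stopping rule in Section 10.3.1 counts the same events.

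**Inputs for coverage.**
- Dose days (Section 3.2.2.1): 1, 2, 8, 9, 15, 16 in each of 8 cycles, so 6 × 8 = 48 planned doses.
- Lab days (Section 3.3.7.2): 5 in cycle 1 plus 7 Day 1 visits in cycles 2-8, so 12. Cycle 1 day 22 is not a dose day, which leaves 11 on dose days.

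**Matching doses to scheduled labs.**

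| Reading | Cycle 1 | Cycles 2-8 | Total covered | No scheduled lab |
|---|---|---|---|---|
| Lab on the same day | 4/6 | 7/42 | 11/48 (23%) | 37 |
| One draw serves both consecutive dose days | 6/6 | 14/42 | 20/48 (42%) | 28 (58%) |

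On the lenient reading, cycle 1 days 9 and 16 are served by days 8 and 15, and day 2 of each later cycle by day 1. What remains is 4 days × 7 cycles = 28 doses. Accepting a lab up to six days old does not change the 20. Accepting one seven days old adds day 8 of cycles 2-8 (7 doses), giving 27 covered and 21 not.

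By dosing week, 8 × 3 = 24 weeks are planned. Scheduled labs fall in 3 + 7 = 10 of them, and 14 have none.

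**Timing of the scheduled counts.** In cycles 2-8 the next Day 1 is day 29 of the cycle before. It nominally follows 12 days without carfilzomib (days 17-28) and 7 without lenalidomide (days 22-28). Dexamethasone is still given on days 22 and 23, so the interval is not wholly free of drug.

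**The case against.** The best defense is a dilemma. If Section 4.1.2 covers every dose, the mid-cycle counts are already required and the holds have their data. If it does not, nothing conflicts. Section 3.3.7.2 does not claim to list every lab, Section 3.3.7.6 permits more, and a site could satisfy all three. Section 4.1.2 also belongs to the tumor lysis guidance and does not speak of each dose.

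Part of this stands: counts may well exist where sites acted on Section 4.1.2, so the data are unscheduled rather than necessarily absent. But neither branch leaves the text sound. On the first, the calendar omits required labs. On the second, the cycle 2-8 holds have no scheduled trigger. Testing on clinical grounds is discretionary and does not meet a mandatory review.

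Two further objections stand as limits. Section 6.1 counts an abnormal laboratory value as an adverse event only under listed conditions, so a brief symptomless fall might go unreported even with frequent sampling. And Section 13.1.1 describes carfilzomib supply during treatment in the past tense, so induction appears to be over.

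A reader might also infer a clash between the 2-day lab window and calendar footnote p: "Variations of +/- 3-14 days of scheduled visits are permitted". The documents do not support this. The footnote moves the visit, and the lab window is anchored to Day 1 and moves with it.

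**Conclusion.** The passages need reconciling. On the reading most favorable to the plan that still ties a draw to its own pair of dose days, 28 of 48 planned carfilzomib doses have no scheduled lab, all in cycles 2-8. On a same-day reading it is 37. Cycle 1 is complete on the lenient reading. This assumes all eight cycles are given as planned. It also assumes that footnote a to the Routine Labs row, whose text was not available to me, does not add lab days; Section 3.3.7.2 is complete and agrees with the calendar columns.

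The effect is on the dosing safety checks and on descriptive hematologic toxicity rates. Two stronger readings are tempting:

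- That the primary endpoint is biased. The neurologic decision and stopping rules use no blood counts, so it is not.
- That blood-count toxicity is measured mainly at recovery. This is an inference from the dosing gap before Day 1. The documents give no nadir timing, and counts from other days may exist.

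Nor can a number of missed events be derived. The 17% rates of grade 3 or worse thrombocytopenia and neutropenia in Section 1.2.6 come from another study with several dose levels and a median of 12 cycles.

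**What to change.** Reconcile Section 3.3.7.2, the calendar's Routine Labs row and Section 4.1.2 so that one rule states which carfilzomib days need reviewed labs, and refer to it from Section 3.3.2.5. Which days those should be is a clinical decision for the sponsor and is not proposed here.

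In the toxicity report, grade every available blood count by CTCAE, scheduled or not, and show the result alongside the events that meet the Section 6.1 laboratory rule. State that cycle 2-8 cytopenia rates may be underestimates where only Day 1 counts exist.

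The cost is protocol and calendar wording, plus more laboratory data to enter. With carfilzomib treatment apparently complete, the wording change mainly corrects the record; the reporting change is the part that still has effect.
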